6.1.3 Secondary Efficacy Endpoints

[Phase 1 part]

Not applicable.

[Phase 2 part]

- Overall survival (OS)

OS is defined as the time from start date of the first treatment until the date of death due to any cause. For a subject who is not known to have died by the end of long-term follow-up, OS is censored at the date of last known alive.

As a sensitivity analysis, OS is defined similarly as the above, however, subjects who undergo HSCT will be censored at the time of HSCT.

- Event free survival (EFS)

The time from the date of start date of the first treatment until the date of documented relapse after CR, treatment failure or death from any cause, whichever occurs first. For a subject with none of these events, EFS is censored at the date of last disease assessment. Subject without post-treatment disease assessment will be censored at the start date of the treatment.

Treatment failure includes those subjects who failed to achieve CRc by the end of consolidation period, or who discontinued the treatment due to “lack of efficacy” without a previous response.

Treatment failure date refers to the end of treatment date for subjects with treatment failure.

- Relapse free survival (RFS)

The time from the date of achievement of first CRc until relapse or death from any cause, whichever comes first for subjects who achieve CRc. For a subject who is not known to have relapsed or died, RFS is censored on the date of last relapse-free disease assessment date.

Last relapse-free disease assessment date refers to the subject’s last disease assessment date.

- CR rate after each treatment therapy

Defined as the number of subjects who achieve the best response of CR divided by the number of subjects in the analysis population after each treatment therapy period.

Subjects with unknown or missing response, or who provide no information on response will be treated as non-responders and will be included in the denominator when calculating rates.

- CR rate without MRD after each treatment therapy

Defined similarly as CR rate after each treatment therapy. Responders achieve that the best response is CR and MRD status is negative. CRc rate without MRD after each treatment therapy will also be defined similarly.

- CRh rate after each treatment therapy

Defined similarly as CR rate after each treatment therapy.

- CRc (Composite CR) rate after each treatment therapy

CRc: CR + CRp + CRi

Defined similarly as CR rate after each treatment therapy.

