6.1.4 Exploratory Efficacy Endpoints

[Phase 1 part]

- CR rate
Defined as the number of subjects with CR divided by the number of subjects in the analysis population. Subjects with unknown or missing response, or who provide no information on response at the end of study will be treated as non-responders and will be included in the denominator when calculating rates.
- CRp rate
Defined similarly as CR rate.
- CRi rate
Defined similarly as CR rate.
- CRc rate
Defined similarly as CR rate.
- PR rate
Defined similarly as CR rate.
- Overall response rate: CRc + PR
Defined similarly as CR rate.
- Duration of response – Duration of response is defined as the period from the first date of achieving CR, CRp, CRi, or PR to the first date of documented relapse for subjects who achieve CR, CRp, CRi, or PR. Subjects who die without report of relapse are considered non-events and censored at their last relapse-free disease assessment date. Other subjects who do not relapse on study are considered non-events and censored at the last relapse-free disease assessment date.
- Duration of CR is defined similarly as duration of response for subjects who achieved CR.
- Duration of CRc is defined similarly as duration of response for subjects who achieved CRc.

[Phase 2 part]

- Transplantation rate
Transplantation rate is defined as the percentage of subjects undergoing HSCT during the study period.
- Cumulative incidence of relapse (CIR) after 1st CR (CR1)
Defined as the time from the date of achieving CR1 until relapse. When calculating this variable, only subjects who achieved CR1 are included. Subjects alive without relapse will be censored on the date of last relapse-free disease assessment date. Although subjects who died without relapse should be treated as the subjects who occurred competing event, those

subjects will be censored at the date of death.

- Cumulative incidence of death (CID) after CR1

Defined as the time from the date of achieving CR1 until death. When calculating this variable, only subjects who achieved CR1 are included. Subjects who are alive without death will be censored at the date of last known alive.

- Time to hematopoietic recovery after each treatment cycle

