As a sensitivity analysis, response assessment will be defined similarly as the above analysis, however, all response assessment data will be used even if there were subjects who undergo HSCT (i.e. response assessment data after HSCT will also be used).

Time-to-event variables:

For time-to-event variables efficacy analysis will be summarized using descriptive statistics. The survival curve and the median will be estimated using the Kaplan-Meier method and will be reported along with the corresponding 95% CIs. Kaplan-Meier plot will be presented.

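### CID after CR1 is all-cause death and so is not the counterpart of CIR; death without relapse, which the SAP names as the competing event, is not estimated as an incidence anywhere

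*SAP*

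**What the plan says.** Section 6.1.4 lists two Phase 2 exploratory endpoints one after the other, both restricted to subjects who achieved CR1.

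- **CIR after CR1**: "Defined as the time from the date of achieving CR1 until relapse". On deaths in remission the item says "Although subjects who died without relapse should be treated as the subjects who occurred competing event", and then that those "subjects will be censored at the date of death".
- **CID after CR1**: "Defined as the time from the date of achieving CR1 until death". The only censoring rule is "Subjects who are alive without death will be censored at the date of last known alive". Relapse is not mentioned.

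For comparison, section 6.1.3 has "OS is defined as the time from start date of the first treatment until the date of death due to any cause", and for subjects not known to have died, "OS is censored at the date of last known alive".

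Section 7.4 sets one method for all Phase 2 time-to-event variables: "The survival curve and the median will be estimated using the Kaplan-Meier method". It names no cumulative incidence function.

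**The concern.** CIR and CID share an origin and a population, and the CIR item itself identifies death without relapse as the event that competes with relapse. A reader will naturally take CID to be the incidence of that competing event. As defined, it is not. A subject who relapses and then dies is an event in CIR (at relapse) and again in CID (at death), so the two do not divide the failures after CR1 between them.

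What is at stake is interpretation. After intensive chemotherapy with ASP2215, one wants to know how many remissions are lost to relapse and how many to death in remission. A high CID could be read as death in remission when much of it is death after relapse. This would remain even if the censoring of deaths in CIR, a separate matter, were corrected.

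**Working it through.** **1. What CID is.** The SAP states no figure for CID or CIR, so there is none to reproduce; the first check compares definitions.

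| | Event | Origin | Population | Censoring |
|---|---|---|---|---|
| CID (6.1.4) | Death | CR1 | Subjects with CR1 | Last known alive |
| OS (6.1.3) | Death, any cause | First treatment | TTE-FAS (7.4) | Last known alive |

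Event and censoring rule are the same. Restart OS at CR1 in subjects with CR1, and 1 - Kaplan-Meier for CID is exactly 1 - OS from CR1.

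**2. Whether death without relapse is estimated elsewhere.**

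- CIR (6.1.4): censored at death.
- Duration of CR (6.1.3): a non-event, censored at the last relapse-free assessment.
- RFS and EFS (6.1.3): counted, but only within a composite.
- Adverse event tables (7.5.2): deaths and TEAEs leading to death are counted and all deaths are listed, but not by remission status and not as an incidence from CR1.

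No endpoint gives it as an incidence.

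**3. Size.** All rates here are assumptions. Take constant yearly hazards r (relapse), d (death in remission) and p = ln 2 / median survival after relapse, read at t = 3 years. Let L = r + d.

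- CIR = (r/L)(1 - exp(-Lt))
- Death without relapse = (d/L)(1 - exp(-Lt))
- Relapsed and alive = r(exp(-Lt) - exp(-pt))/(p - L)
- Death after relapse = CIR - relapsed and alive
- CID as written = death without relapse + death after relapse

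Worked case: r = 0.25, d = 0.05, median 0.5 year, so L = 0.30 and p = 1.3863.

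- 1 - exp(-0.9) = 0.593430, the proportion failed by relapse or death
- CIR = 0.8333 x 0.593430 = 0.494525
- Death without relapse = 0.1667 x 0.593430 = 0.098905
- Relapsed and alive = 0.25 x (0.406570 - 0.015625)/1.086294 = 0.089972
- Death after relapse = 0.494525 - 0.089972 = 0.404553
- CID as written = 0.098905 + 0.404553 = 0.503458
- Share of CID that is death after relapse = 0.404553/0.503458 = 80%

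All eight combinations, in % at 3 years (rows may differ by 0.1 from rounding):

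| r | d | Median after relapse (years) | Death without relapse | Death after relapse | CID as written | Share after relapse |
|---|---|---|---|---|---|---|
| 0.15 | 0.05 | 0.5 | 11.3 | 27.1 | 38.4 | 71 |
| 0.15 | 0.05 | 1 | 11.3 | 20.9 | 32.2 | 65 |
| 0.15 | 0.10 | 0.5 | 21.1 | 25.6 | 46.7 | 55 |
| 0.15 | 0.10 | 1 | 21.1 | 19.9 | 41.0 | 49 |
| 0.25 | 0.05 | 0.5 | 9.9 | 40.5 | 50.3 | 80 |
| 0.25 | 0.05 | 1 | 9.9 | 31.5 | 41.4 | 76 |
| 0.25 | 0.10 | 0.5 | 18.6 | 38.4 | 56.9 | 67 |
| 0.25 | 0.10 | 1 | 18.6 | 30.0 | 48.6 | 62 |

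**4. Cross-check with other assumptions.** Fix the 36-month incidences instead, at 40% relapse and 10% death in remission, with a 6-month median after relapse. CID as written is then 42.2% (42.3% as 1 - Kaplan-Meier in 400,000 simulated subjects), of which 32.3 points are deaths after relapse. Over relapse 30-50%, death in remission 5-20% and median 6-12 months, CID as written is 23-62%.

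**The case against.** The definition is complete and coherent. Event, origin, population and censoring are all stated; all-cause death has no competing event, so Kaplan-Meier is valid for the quantity defined. The SAP never says that CIR and CID divide the failures after CR1 or that CID means death in remission, and the competing-event sentence belongs to the CIR item alone. All of this stands, so a reader should not infer that the CID estimate is biased or that the two items contradict each other.

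Three further inferences are tempting and not supported:

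- That CID merely repeats OS. OS runs from first treatment and includes subjects who die in induction or never reach CR; CID is conditional on CR1 and starts there. The identity holds only for OS restarted at CR1.
- That deaths in remission would be invisible. Long-term follow-up collects relapse, remission status, and cause and date of death (section 3.2), and all deaths are listed. In about 80 subjects they could be identified one by one. TEAEs leading to death are also tabulated by relationship to ASP2215 and to the regimen, although TEAEs are in general limited to 30 days after the last dose (section 6.2). What is lacking is an incidence.
- That most CID events must be deaths after relapse. Over the assumed range the share falls as low as 49%.

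Nor should CIR and CID be added to make the case. In the worked example, 49.5% + 50.3% = 99.8% pairs a properly estimated CIR with CID as written. The SAP's own CIR censors deaths and would give 1 - exp(-0.75) = 52.8%.

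The objection does not remove the gap: the SAP names death without relapse as the competing event and then gives no estimate of it.

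**Conclusion.** The point holds as a specific improvement to an exploratory endpoint. By definition, CID after CR1 is one minus overall survival from CR1, and subjects who relapse and then die are events in both CIR and CID. Death without relapse has no incidence estimate of its own. These statements follow from the wording and need no assumed rates.

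The size does rest on assumptions: constant hazards in the stated ranges, read at 3 years. CID as written is then 32-57%, against 10-21% for death without relapse, and 49-80% of CID events are deaths after relapse. Actual rates may differ, but whenever deaths follow relapse, CID exceeds the incidence of death in remission.

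The primary analysis of the CR rate is unaffected, and the SAP attaches no test or threshold to CID.

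**What to change.** In section 6.1.4, define CID as death without prior relapse after CR1, with relapse as the competing event. In section 7.4, state that CID and CIR are both estimated by the Aalen-Johansen cumulative incidence function. CIR, CID and relapse-free survival from CR1 then sum to 100%. This is relapse-free survival in subjects with CR1, timed from CR1; the SAP's RFS endpoint starts at first CRc and will not match it exactly. If all-cause death from CR1 is also wanted, keep it with Kaplan-Meier under that name.

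The cost is SAP wording and a standard option in the program. Relapse and death dates are already collected. The downside is that CID will have fewer events and a wider relative confidence interval.

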6 ANALYSIS VARIABLES

6.1 Efficacy Endpoints

6.1.1 Response Definition

Antitumor response will be assessed on the days of bone marrow sampling based on the bone marrow findings, and peripheral blast count, neutrophil count, and platelet count. Preferably, samples from both bone marrow aspiration and biopsy should be obtained, but if the bone marrow aspiration was determined to be sufficient, biopsy may be omitted.

Antitumor response is defined per modified Cheson criteria (2003) or modified ELN recommendations (2017) as outlined below [Döhner et al, 2017; Cheson et al, 2003].

[Phase 1 part]

The assessment will be performed by the investigator. The results of bone marrow findings and peripheral blast count will be entered into the eCRF.

[Phase 2 part]

Bone marrow aspiration and/or biopsy samples and hematology samples are evaluated both centrally and locally. If bone marrow samples were obtained for unscheduled visits, those samples along with hematology samples should be submitted for central assessment.

Definitions

Complete Remission (CR):

CR is defined as a morphologically leukemia-free state at the post-baseline visit, having a neutrophil count of $\geq 1,000/\text{mm}^3$ and platelet count of $\geq 100,000/\text{mm}^3$, bone marrow myeloblasts $< 5\%$. There must be no evidence of Auer rods and no evidence of extramedullary leukemia. The blast counts in peripheral blood must be $\leq 2\%$.

Complete Remission with Partial Hematologic Recovery (CRh):

CRh is defined as a condition at the post baseline visit, having bone marrow myeloblasts $< 5\%$, partial hematologic recovery neutrophil count $\geq 500/\text{mm}^3$ and platelet count $\geq 50,000/\text{mm}^3$, no evidence of extramedullary leukemia and cannot be classified as CR. The blast counts in peripheral blood must be $\leq 2\%$.

Complete Remission with Incomplete Platelet Recovery (CRp):

CRp is defined as a condition that meets all of the CR criteria at the post-baseline visit, except for the unrecovered platelet count ($< 100,000/\text{mm}^3$).

Complete Remission with Incomplete Hematological Recovery (CRi):

CRi is defined as a condition that meets all of the CR criteria at the post-baseline visit, except for the unrecovered neutrophil count ($< 1,000/\text{mm}^3$) whether or not having unrecovered platelet counts).

Partial Remission (PR):

At a post-baseline visit, PR is defined as a condition with regeneration of normal hematopoietic cells in the bone marrow.

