Defined as the time from the date of start date of the treatment until the date of having a neutrophil count of $\geq 1,000/\text{mm}^3$ and platelet count of $\geq 100,000/\text{mm}^3$. Subjects with none of these events are censored at the date of last assessment within each treatment cycle.

- MRD

MRD is defined as binary endpoint, negative or positive. More detail of the definition is in Section 6.5. MRD rate is defined as the percentage of subjects whose MRD is negative.

- MR

MR is defined as binary endpoint, MR or no MR. More detail of the definition is in Section 6.5. MR rate is defined as the percentage of subjects who achieve MR.

- MRD-negative CR rate after induction

Defined as the number of subjects who achieve the best response of CR and whose MRD is negative during induction period divided by the number of subjects in the analysis population during induction therapy period. Subjects with unknown or missing response, or who provide no information on response will be treated as non-responders and will be included in the denominator when calculating rates.

- Overall MRD-negative CR rate for any treatment period

Defined as the number of subjects who achieve the best response of CR and at least one post-baseline MRD is negative divided by the number of subjects in the analysis population. If subjects have multiple MRD samples collected across different timepoints, the overall MRD status is negative if there is at least one MRD sample is negative and the overall MRD status is positive if all available MRD samples are positive. Subjects with unknown or missing post-baseline MRD status, or who provide no information on post-baseline MRD status will be treated as MRD positive and will be included in the denominator when calculating rates.

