7.5.3 Clinical Laboratory Evaluation

Analysis set: SAF

All clinical laboratory evaluations including hematology and bone marrow, biochemistry, coagulation and urinalysis will be performed locally (for Phase 2 par, both centrally and locally).

The baseline visit is the last measurement taken prior to initial treatment.

Quantitative clinical laboratory variables, i.e. hematology, biochemistry, coagulation and urinalysis will be summarized using mean, standard deviation, minimum, maximum and median by measurement time point. Additionally, a within-subject change will be calculated as the post-baseline measurement minus the baseline measurement and summarized in the same way. Each laboratory result will be classified as L, N, or H by measurement time point according to supplied reference ranges. SI unit will be used for display. Summary shifts in each laboratory test result will be presented by measurement time point.

The number and percentage of subjects below and above reference range will be summarized by measurement time point.

Frequency tabulations of qualitative clinical laboratory variable (urinalysis) will be presented by measurement time point.

For hematology and biochemistry two types of shift tables will be presented:

- Shift tables of reference range changes from baseline to each treatment visit (low, normal, high), and
- Summary shifts of reference range changes from baseline to each treatment visit (shift from normal or high to low, shift from normal or low to high, categorized increase [shift from low to normal or from normal to high], categorized no change [value stays in the same reference range], categorized decrease [shift from high to normal or from normal to low]).

Laboratory results will also be graded using NCI-CTCAE, where possible. Parameters that have criteria available for both low and high values, i.e., hypo- and hyper-, will be summarized for both criteria. The same subject can be counted for both values if the subject has different laboratory values meeting each criterion. NCI-CTCAE grade of laboratory evaluations will be summarized by number and percentage of subjects by measurement time point. Shift tables of NCI-CTCAE grade change from baseline to worst post-baseline grade will also be presented.

Bone marrow results will be listed only.

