Cycle 1 Day 1 10 hours post-dose	Day 1	Scheduled date, scheduled time \pm 20 minutes	
Cycle 1 Day 1 24 hours post-dose	Day 2	Scheduled date, scheduled time \pm 60 minutes and prior to Day 2 dosing	Blood sampling for ASP2215 and cytarabine
Cycle 1 Day 6 pre-dose	Day 6	Scheduled date, within 30 minutes before dosing	
Cycle 1 Day 15	Day 15	Scheduled date - 1 day	Blood sampling for ASP2215. If performed on Day 14 within the allowed visit window [-1] for Day 15, blood sampling will be performed at pre- dose.
End of treatment (for any period)	Date of judgment of discontinuation	Scheduled date + 7 days	Blood sampling for ASP2215 is strongly recommended if possible

Both in the induction and consolidation periods, blood sampling for PK analysis is performed only during Cycle 1.

- Visit Windows for FLT3 Mutation Test

Induction period			
Assessment timing	Scheduled date	Acceptable time range	Remarks
Screening	—	7 days before dosing – 1 day before dosing (Before dosing if the screening and Day 1 of Cycle 1 overlap).	
Consolidation period			
Assessment timing	Scheduled date (Day 1: Cycle 1 Day 1 Start of treatment)	Acceptable time range	Remarks
Cycle 1 Day 1	Day 1	Scheduled date + 7 days	Performed only for Cycle 1 of consolidation period
Maintenance period			
Assessment timing	Scheduled date (Day 1: Cycle 1 Day 1 Start of treatment)	Acceptable time range	Remarks
Cycle 1 Day 1	Day 1	Scheduled date	

[Phase 2 part]

All analyses except for the analysis based on central laboratory data will be based on CRF visit except for the baseline. The baseline visit is the last measurement taken prior to initial treatment.

For the analysis based on central laboratory data, visit windows are allowed for certain visits per the schedule of assessments. Subject data will not be excluded from analyses due to the subject's failure to comply with the visit schedule. The visit windows for assessments are described in the following table.

CRF visit	Visit Window
Induction Day 8	Scheduled day
Induction Day 15	D15 ± 2
Induction Day 21	D21 ± 2
Induction Day 28	D28 + 7
Induction Day 42	D42 + 7
Induction Day 56	D56 + 7
Consolidation Day 8	Scheduled day
Consolidation Day 15	D15 ± 2
Consolidation Day 21	D21 + 7
Maintenance Cycle 2 Day 1	(Maintenance Cycle 1 Day 1+28) ± 7
Maintenance Cycle 5 Day 1	(Maintenance Cycle 1 Day 1+112) ± 7
Maintenance Cycle 8 Day 1	(Maintenance Cycle 1 Day 1+196) ± 7
Maintenance Cycle 11 Day 1	(Maintenance Cycle 1 Day 1+280) ± 7

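### Time to hematopoietic recovery (Phase 2, exploratory) does not require counts to have fallen first, so a cycle that falls and never recovers can be coded as an early recovery

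*SAP*

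**What the plan says.** The endpoint is listed in SAP Section 6.1.4 among the Phase 2 exploratory endpoints as "Time to hematopoietic recovery after each treatment cycle". Its definition reads "Defined as the time from the date of start date of the treatment until the date of having a neutrophil count of" at least 1,000/mm³, combined with platelets of at least 100,000/mm³. The censoring rule is "Subjects with none of these events are censored at the date of last assessment within each treatment cycle".

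Section 6.1.1 uses the same two count cut-offs for CR: "CR is defined as a morphologically leukemia-free state at the post-baseline visit, having a neutrophil count of" at least 1,000/mm³, again with platelets of at least 100,000/mm³.

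For the analysis, Section 7.4 says of time-to-event variables in general: "The survival curve and the median will be estimated using the Kaplan-Meier method and will be reported along with the corresponding 95% CIs". It adds no rule specific to this endpoint. Section 7.11.5 assigns Phase 2 observations to visits and says nothing about which counts can qualify as a recovery.

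**The concern.** Recovery in ordinary use means a return after a fall. The operational rule contains only the return: any date in the cycle with both counts at or above the cut-offs is an event, and only a cycle with no such date can be censored. It sets no low point, no earliest eligible day and no exclusion of the Day 1 count.

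Because the cut-offs are those of CR, a subject in CR whose counts hold enters the next cycle already meeting the event. Two errors can follow:

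- A cycle that is still above both cut-offs at an early count, then falls and does not recover, has a qualifying date. It is counted among the fastest recoveries when it should be censored.
- A cycle that falls and later recovers gets the pre-fall date if the first qualifying date is used. The SAP does not say which date that is. It refers to the date of having the counts, whereas for relapse-free survival it does specify a first occurrence: "The time from the date of achievement of first CRc until relapse or death from any cause".

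At stake are the reported recovery curve and median for this descriptive endpoint.

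**Working it through.** The SAP gives no figure for this endpoint, so there is none to reproduce. The check applies the rule to constructed cycles and then sizes the effect on assumed inputs.

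**Step 1. The rule applied to single cycles.** Counts are invented (neutrophils/platelets per mm³). The first qualifying date is used.

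| Cycle | Day 1 | Day 8 | Day 15 | Day 21 | Day 28 | As written | Prior fall required |
|---|---|---|---|---|---|---|---|
| A | 2,500/180,000 | 1,400/110,000 | 100/15,000 | 300/30,000 | 700/60,000 | event Day 1 | censored Day 28 |
| B | not used | 1,400/110,000 | 100/15,000 | 300/30,000 | 700/60,000 | event Day 8 | censored Day 28 |
| C | not used | 600/70,000 | 100/15,000 | 300/30,000 | 700/60,000 | censored Day 28 | censored Day 28 |
| D | not used | 1,400/110,000 | 100/15,000 | 300/30,000 | 1,200/120,000 | event Day 8 | event Day 28 |

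A and B never recover but are events. D recovers but its time is too short. C shows that the rule works when the first count used is already low.

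**Step 2. Inputs for the size.**

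- From Section 7.11.5 (Phase 2 central-laboratory windows, consolidation): Day 8, Day 15 ± 2, Day 21 + 7. The last visit is therefore on Day 21 to 28, that is 20 to 27 elapsed days. Day 8 is 7 elapsed days.
- Assumed: the clock starts on Day 1 of the cycle; every cycle is below a cut-off at Day 15; a share *a* is above both cut-offs at Day 8; a share *r* has not recovered by the last visit, independently of *a*.

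**Step 3. All last visits on one day.** The Kaplan-Meier share recovered is 1 − r(1 − a) as written and 1 − r with a prior fall required. The difference is a × r.

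**Step 4. Last visits spread evenly over the eight days 20 to 27, independently of recovery.** When *m* of the eight days remain, 1/*m* of the cycles at risk have their last visit, and 1 − r of those are events. With a prior fall required, the share not recovered is the product over m = 1 to 8 of (1 − (1 − r)/m). For r = 20%:

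0.2 × 0.6 × 0.7333 × 0.8 × 0.84 × 0.8667 × 0.8857 × 0.9 = 0.0409, so 95.9% recovered.

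As written, with the first date used, a share *a* leaves at 7 days and the rest follow the same pattern. The share not recovered is (1 − a) × 0.0409, and the overstatement is a × 4.09 points.

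| r = 20% | a = 10% | a = 25% | a = 40% | a = 60% |
|---|---|---|---|---|
| One day: as written | 82% | 85% | 88% | 92% |
| One day: overstatement vs 80% | 2 | 5 | 8 | 12 |
| Spread: as written | 96.3% | 96.9% | 97.5% | 98.4% |
| Spread: overstatement vs 95.9% | 0.4 | 1.0 | 1.6 | 2.5 |

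The spread figures are higher because cycles censored on an early day leave the risk set before others recover. Kaplan-Meier then no longer equals the crude proportion.

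**Step 5. Median, r = 20%, spread visits, first date.** With a prior fall required, the curve is 0.580 at 23 days and 0.464 at 24, so the median is 24. As written with a = 25%, it is 0.75 × 0.691 = 0.518 at 22 days and 0.75 × 0.580 = 0.435 at 23, so the median is 23. At a = 40% it is 21.

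**The case against.** The strongest reply is that the title says recovery, which presupposes a fall, and that any programmer would understand it so. This is fair as to intent. But the derivation is coded from the definition and the censoring rule, and neither carries the condition.

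The second reply concerns the time origin. The SAP does not say which treatment start is meant. Its key terms describe Phase 2 subjects who received chemotherapy but never ASP2215, because they had not met all criteria by day 8. If the induction clock started at the first ASP2215 dose, a Day 8 count taken before that dose would not lie after the origin, and a cycle like B need not be an event. This stands. A reader might infer that the error occurs wherever the clock starts, but the documents do not support that. It needs a count after the clock starts that is still above both cut-offs.

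The third reply concerns size. A reader might take the 2 to 12 points as the general effect, or suppose that the median moves only when more than half the cycles are high at Day 8. Both hold only when all last visits fall on one day (the median statement also needs the first-date reading), and the SAP's own window allows Day 21 to 28. Nor does the recovered share stay the same whichever qualifying date is taken: with spread visits, r = 20% and a = 60%, it is 98.4% on the first date and 98.7% on the later one.

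Finally, the endpoint is exploratory, descriptive and untested. That is correct and limits the weight of the point.

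**Conclusion.** The point holds as a defect in a stated rule. A cycle with a count above both cut-offs after the clock starts, followed by a fall without recovery, is coded as a recovery. One that falls and recovers gets too short a time if the first qualifying date is used. The rule gives the intended result whenever the first count used is already below a cut-off.

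The true size is unknown, because the SAP holds no count data. The illustrative overstatement is a × r with one common last-visit day, and about 0.4 to 2.5 points with evenly spread visits, r = 20% and the first qualifying date. Both rest on the assumed shares, on their independence and on a Day 1 clock.

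A reader might infer that the CR result is also inflated, since the cut-offs are shared. It is not: CR also requires marrow and blast criteria and does not use this definition. No test depends on the endpoint. This is a minor clarification that is worth making.

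**What to change.** Amend the definition in Section 6.1.4 so that:

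- time runs from Day 1 of each cycle;
- the event is the first date on which both cut-offs are met after a post-Day-1 count in that cycle below either cut-off;
- cycles with such a fall and no later qualifying count are censored at the last assessment in the cycle;
- the number and percentage of cycles with no observed fall are shown next to the estimate, with a sensitivity estimate that enters them at time 0.

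The low count should be any post-Day-1 count before the qualifying one. Requiring it to be the last low count in the cycle would turn the endpoint into sustained recovery, and a single late dip would cancel a recovery already reached.

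The downside is that the main estimate then describes only cycles with an observed fall, which is selection on something that happens after treatment starts. A fall between visits would also be missed. This is why the count of omitted cycles and the sensitivity estimate are needed. As an example, with r = 20% among the remaining cycles and a no-fall share of 10% or 25%, the sensitivity estimate is 0.10 + 0.90 × 0.80 = 82% or 0.25 + 0.75 × 0.80 = 85%, against 80% in the main estimate (one common last-visit day).

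The cost is SAP wording and derivation code. It uses hematology results already collected.
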